Sample - We will recruit patients referred to general surgery for an elective inguinal hernia repair within Alberta Health Services – Fort Saskatchewan Community Hospital ([name] clinic). Patients meeting the inclusion criteria will be randomized 1:1 to either undergo 6 weeks of prehabilitation exercises + post-surgical follow-up or else usual care. Inclusion criteria include: 1) scheduled to undergo first-time inguinal hernia repair surgery after a physical examination identified signs and symptoms consistent with inguinal hernia (direct or indirect hernia); 2) willingness to participate in a targeted perioperative exercise program; 3) 18+ years of age; 4) no medical contraindications to participation in exercise; and 5) employed full-time and required to lift at least 10kg at work. Specific contra-indications that will be screened for include associated medical conditions that preclude exercise. This includes uncontrolled medical conditions including diabetes, hypertension, vertigo, congestive heart failure, chronic obstructive pulmonary disease, intra-abdominal ascites, or pre-existing malnutrition. We will also screen for previous recurrence of hernia, use of narcotics, bone and joint conditions of the spine or extremities, or history of other abdominal surgeries, which will be exclusionary criteria for the study. Exclusion criteria include: 1) previous inguinal hernia; and 2) Body Mass Index >35 since morbidly obese patients experience more surgical complications.[13]

Sample Size - Since this is a pilot study evaluating feasibility of our intervention and evaluation protocols, we will aim to enrol 30 patients. We will randomize 15 to both the intervention and control groups. Thirty participants has been deemed acceptable to yield confidence intervals whose lower limits can help define the range of plausible values for a subsequent power analysis.[14] This will also provide adequate estimates of enrolment, follow-up rates, information on timing, and variance in our measurement protocol to inform a subsequent randomized controlled trial of the intervention.

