Clinical outcomes will be collected at baseline, before surgery, and following the post-surgical intervention by a researcher not involved in the delivery of the intervention. Persistent post-surgical will be defined as pain lasting longer than 3 months post-surgery as per the IASP definition.[15] We will measure pain intensity ratings on a 0-10 Numeric Pain Scale. We will also measure pain-related disability using the Pain Disability Index and SF-12 measures. Lastly, after the operation we will administer the hernia-specific Carolinas Comfort Scale (CCS).[16] The CCS is a widely used hernia-specific patient reported outcome measure that focuses on mesh-related symptoms.[17] We will also measure quality of life and factors linked to chronic pain such as coping strategies, catastrophizing and Kinesiophobia.

Safety and adverse effects – At the weekly sessions, we will as about both exercise completion as well as any symptoms or adverse events experienced. These will be documented. Any post-surgical complications severe enough to warrant referral to the surgeon or ultrasound imaging will also be tracked. Since the ultrasounds are only being done to rule out hernia recurrence as part of routine clinical care, this will be done and interpreted by a radiologist. All patients will also undergo a consult with the surgeon at 1-week, 1-month, and 3-month follow-up as per usual practice.

Plan for Data Analysis

A sample size of 30 participants will yield confidence intervals whose lower limits can help define the range of plausible values for a subsequent power analysis program. This will guarantee the timely and on-budget completion of the study. All analyses will be conducted using STATA 14.2. Descriptive analysis will be used to report feasibility outcomes (e.g. recruitment rates, adherence, etc.) and identify trends of clinical outcomes. Feasibility targets will be evaluated as per the Appendix.

See Attached Study Protocol for the full list of references.

- 3.0 Describe procedures, treatment, or activities that are above or in addition to standard practices in this study area (eg. extra medical or health-related procedures, curriculum enhancements, extra follow-up, etc): The Prehab program discussed above that we are studying is in addition to the standard surgical practices in this study area.

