4.2 Of these, how many are controls, if applicable?

0

4.3 If this is a multi-site study, how many participants do you anticipate will be enrolled in the entire study?

5.0 Justification for sample size:

Since this is a pilot study evaluating feasibility of our intervention and evaluation protocols, we will aim to enrol 30 patients. We will randomize 15 participants to each group. Thirty participants has been deemed acceptable to yield confidence intervals whose lower limits can help define the range of

plausible values for a subsequent power analysis. This will also provide adequate estimates of enrolment, follow-up rates, information on timing, and variance in our measurement protocol to inform a subsequent randomized controlled trial of the intervention.

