There are no items to display

5.0 Questionnaires, Cover Letters, Surveys, Tests, Interview Scripts, etc.:

	Document Name	Versio	n Date	Description
ூ ↔	Assessment booklet V4.docx	0.03	2021-03-02 4:44 PM	
9	Feedback Survey	0.01	2021-03-02 4:44 PM	
9	Functional Testing Form	0.01	2021-03-02 4:45 PM	
9	Adherence and Adverse Events Form	0.01	2021-03-02 4:46 PM	
5	CLEAN Assessment booklet V4.docx	0.01	2021-03-03 7:48 AM	

6.0 Protocol/Research Proposal:

	Document Name		Date	Description
ூ ↔	Full proposal	0.04	2021-01-13 12:57 PM	
9	Data Collection Timeline and Protocol	0.01	2021-03-02 4:45 PM	
9	Exercise Protocol	0.01	2021-03-02 4:46 PM	

7.0 Investigator Brochures/Product Monographs:

Document Name Version Date Description

There are no items to display

8.0 Health Canada No Objection Letter (NOL):

Document Name Version Date Description

There are no items to display

9.0 Confidentiality Agreement:

Document Name Version Date Description

There are no items to display

10.0 Conflict of Interest:

Document Name Version Date Description

There are no items to display

11.0 Other Documents:

For example, Study Budget, Course Outline, or other documents not mentioned above

	Document Name	Version	Date	Description
9	Appendix with Feasibility Criteria	0.02	2021-01-13 12:25 PM	

Final Page

You have completed your ethics application! Click "Continue" to go to your workspace.

This action will NOT SUBMIT the application for review.

Only the Study Investigator can submit an application to the REB by selecting the "SUBMIT STUDY" under My Activities after you click CONTINUE.

APPENDIX 2

FEASIBILITY AND ACCEPTABILITY CRITERIA							
Proceed	Proceed with Protocol Amendments	Significant Amendments Required					
Recruitment							
n=30 within 4 months	n ≥ 15 within 8 months	n < 10 within 8 months					
50% of eligible participants consent to participate	40% of eligible participants consent to participate	25% of eligible participants consent to participate					
Exercise program							
60% of participants report exercise at least 3 times a week	40% of participants report exercise at least 3 times a week	25% of participants report exercise at least 3 times a week					
Content Acceptability							
50% found treatment useful (Likert ≥ 4/5)	25% found treatment useful (Likert ≥ 4/5)	< 25% found treatment useful (Likert ≥ 4/5)					
50% found treatment helpful (Likert ≥ 4/5)	25% found treatment helpful (Likert ≥ 4/5)	< 25% found treatment helpful (Likert ≥ 4/5)					

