Format Acceptability							
50% found treatment delivery (in-person and home) acceptable (Likert ≥ 4/5)	25% found treatment delivery acceptable (Likert ≥ 4/5)	< 25% found treatment delivery acceptable (Likert ≥ 4/5)					
50% reported being likely to recommend this treatment	25% reported being likely to recommend this treatment	< 25% reported being likely to recommend this treatment					
50% reported being likely to use this treatment again	25% reported being likely to use this treatment again	< 25% reported being likely to use this treatment again					

Follow Up						
90% of participants followed up at the end of Prehab	50% of participants followed up at the end of Prehab	25% of participants followed up at the end of Prehab				
80% of participants followed up at 3 months	50% of participants followed up at 3 months	25% of participants followed up at 3 months				
Treatment						
70% of participants attended all treatment sessions	50% of participants attended all treatment sessions	25% of participants attended all treatment sessions				
70% of sessions were compatible with participant's work/activity schedule	50% of sessions were compatible with participant's work/activity schedule	25% of sessions were compatible with participant's work/activity schedule				
Burden						
75% of participants found the burden of completing questionnaires Likert <3/10 (0 = no burden, 10 = most burden)	50% of participants found the burden of completing questionnaires Likert <3/10 (0 = no burden, 10 = most burden)	25% of participants found the burden of completing questionnaires Likert <3/10 (0 = no burden, 10 = most burden)				
Adverse Events						
No adverse event	1 adverse event related to re- injury	2 or more adverse events

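### Does justifying n = 30 by confidence-interval lower limits, while judging feasibility tiers on bare percentages, leave a gap that the plan must close?

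*Combined protocol and SAP*

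**What the plan says.** Section 2.1 (Sample Size) states that "we will aim to enrol 30 patients" and "We will randomize 15 to both the intervention and control groups". The reason given is that this number yields "confidence intervals whose lower limits can help define the range of plausible values for a subsequent power analysis", with a literature reference. The same reasoning returns as the opening line of the Plan for Data Analysis in section 2.1, and again in section 4.2, item 5.0. Sections 2.1 and 4.2 then add a separate sentence: "This will also provide adequate estimates of enrolment, follow-up rates, information on timing, and variance in our measurement protocol".

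On analysis, section 2.1 says "Descriptive analysis will be used to report feasibility outcomes (e.g. recruitment rates, adherence, etc.) and identify trends of clinical outcomes", followed by "Feasibility targets will be evaluated as per the Appendix". Appendix 2 has three columns: Proceed, Proceed with Protocol Amendments, and Significant Amendments Required. Its entries are percentages, with counts for recruitment number and adverse events. Two Proceed entries are "60% of participants report exercise at least 3 times a week" (middle tier 40%) and "80% of participants followed up at 3 months" (middle tier 50%). No entry mentions a confidence limit, and the adherence row does not say whether participants means the 15 in the intervention arm or all 30.

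**The concern.** A precision argument for a sample size normally says what is being estimated, at what confidence level and how tightly. Here all three are absent, so 30 can be neither reproduced nor refuted. The argument also seems to stop at the sample-size paragraph, because the tiers that steer the next step are read off as observed percentages. In 15 patients an observed percentage is a rough guide to the true one, so a programme could be labelled Proceed or sent for amendment largely by chance.

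There is also a question of direction. A lower limit is the cautious choice for consent, adherence, retention or a treatment effect. For a standard deviation (SD) it is the incautious one, because required sample size grows with its square. Variance is among the quantities the pilot is meant to supply. If the lower-limit wording were applied to it, the later multicentre trial would be too small.

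**Working it through.** **Inputs.** From section 2.1: N = 30, 15 per arm. From Appendix 2: adherence 60% (Proceed) against 40% (middle tier); attendance at all sessions 70% against 50%; treatment useful 50% against 25%; 3-month follow-up 80% against 50%; end-of-Prehab follow-up 90% against 50%. Assumed, because the documents do not say: thresholds are minimums; adherence, attendance and usefulness are judged in the 15 intervention patients; follow-up is judged in all 30; intervals are 95%.

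**The plan's own figure.** N = 30 cannot be recomputed, since no parameter, level, width, SD, effect or power is given. What can be checked is the precision that 30 delivers.

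**Step 1: exact (Clopper-Pearson) 95% intervals at or just above the Proceed thresholds.** For x events in n, the lower limit is the 0.025 quantile of Beta(x, n − x + 1), and the upper limit is the 0.975 quantile of Beta(x + 1, n − x).

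| Item | Count | 95% interval | Contains middle-tier value? |
|---|---|---|---|
| Adherence, in 15 | 9/15 | 32.3% to 83.7% | yes (40%) |
| Adherence, if in 30 | 18/30 | 40.6% to 77.3% | no (40%), narrowly |
| Attendance, in 15 | 11/15 | 44.9% to 92.2% | yes (50%) |
| 3-month follow-up, in 30 | 24/30 | 61.4% to 92.3% | no (50%) |
| End-of-Prehab follow-up, in 30 | 27/30 | 73.5% to 97.9% | no (50%) |

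Near 50%, the half-width is (68.7 − 31.3)/2 = 18.7 points in 30 (15/30) and (78.7 − 26.6)/2 = 26.1 points in 15 (8/15).

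**Step 2: chance of reaching Proceed when the true value equals the middle-tier threshold.** This is P(X ≥ r) for X ~ Binomial(n, p).

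- Adherence: P(X ≥ 9 | 15, 0.40) = 9.5%; if judged in 30, P(X ≥ 18 | 30, 0.40) = 2.1%.
- Attendance: P(X ≥ 11 | 15, 0.50) = 5.9%.
- Useful: P(X ≥ 8 | 15, 0.25) = 1.7%.
- 3-month follow-up: P(X ≥ 24 | 30, 0.50) = 0.07%.
- End-of-Prehab follow-up: P(X ≥ 27 | 30, 0.50) = 0.0004%.

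**Step 3: true values near or at a Proceed threshold.** The error rates are larger here: P(X ≥ 9 | 15, 0.50) = 30%; P(X ≥ 24 | 30, 0.75) = 35%; and adherence truly at 60% misses Proceed with probability P(X < 9 | 15, 0.60) = 39%. A truth of 75% is only 5 points below its cut-off of 80%. Truths that close to a cut-off are often misclassified at any pilot size.

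**Step 4: standard deviation.** The 95% limits as multiples of the estimate are √(df/χ²). With all 30 analysed, df = 28: √(28/44.46) = 0.79 and √(28/15.31) = 1.35. With 12 per arm (80% of 15), df = 22: √(22/36.78) = 0.77 and √(22/10.98) = 1.42. Using the lower limit at 28 df would multiply a later trial's sample size by 28/44.46 = 0.63. That is the size of the mistake if someone made it; it does not show that the plan makes it.

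**Step 5: reading the text.** The lower-limit sentence and the variance sentence are separate, and the second is introduced as an additional benefit. The natural reading is that the lower limits concern a rate or an effect, where they are the cautious side.

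**The case for a change.** The case for a change is that feasibility is the trial's whole purpose and Appendix 2 is its decision rule, so the precision that justifies the sample should have a defined role in that rule, settled before data are seen. With 15 patients, every adherence count from 5 to 13 has a 95% interval containing 60% (5/15 reaches up to 61.6%; 13/15 reaches down to 59.5%). Stating denominators and intervals would cost a few lines and no patients.

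Part of this stands. The rationale is thin, the adherence denominator is unstated, and the one-arm rows are imprecise. But the remedies add little. Promised intervals combined with descriptive reporting already lead an analyst to give counts, denominators and confidence limits; writing that down alters no result. A rule that calls a tier provisional whenever its boundary lies inside the 95% interval would leave 5 to 13 of 15 unresolved, so the adherence row would seldom give a firm answer. A looser one-sided level would be just as debatable a choice. Instructions on which limit to use when sizing the next trial belong in that trial's protocol. The cited reference and the separately listed full proposal are not available here and may supply the missing parameter and level.

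**Conclusion.** The observation is accurate but calls for no change. It is a gap in detail that analysts fill sensibly: no stated number is wrong, and a feasibility pilot of 30 needs no power calculation. The imprecision is real for one-arm items (half-width about 26 points in 15) and moderate for whole-sample items (about 19 points in 30). The claim that the tiers cannot be told apart is too broad: with the truth on the middle-tier threshold, a false Proceed ranges from 9.5% for adherence in 15 to 0.07% for 3-month follow-up in 30. The SD warning is hypothetical, since no section applies a lower limit to a variance. The stakes are also modest: none of the three Appendix 2 columns is a stop, and no efficacy claim rests on them. The conclusion assumes that thresholds are minimums and that denominators are 15 for intervention items and 30 for follow-up. Judging adherence in 30 would sharpen that row (2.1% instead of 9.5%).

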2.1 Study Objectives and Design

1.0 * Provide a lay summary of your proposed research which would be understandable to general public

Inguinal hernia repair is one of the most common surgeries, with more than 20 million performed globally each year. It is estimated that approximately 15% of patients undergoing inguinal hernia repair will experience persistent post-surgical pain that could last months to years. Evidence from related procedures indicates that better surgical preparation through pre-operative exercise and education (i.e. Prehabilitation) followed by ongoing post-surgical rehabilitation leads to more rapid recovery, return to activities and lower likelihood of persistent post-surgical pain. We will determine the feasibility of a peri-operative rehabilitation program (pre- and post-surgery)

and our study protocol for patients undergoing inguinal hernia repair surgery. We hypothesize that: 1) our peri-operative intervention will be feasible and safe to undertake within a clinical setting; 2) we will enrol adequate numbers to justify a larger trial; and that 3) our outcome measurement protocol will provide meaningful information with high response rate and low attrition after 3 months.

Implications

This study is novel and timely given the current healthcare focus on improving strategies for the prevention of chronic pain. The obvious potential benefits for patients with inguinal hernia is the development of a program with the potential to improve post-surgical outcomes and reduce likelihood of post-surgical pain. Our findings will inform a larger, multicenter clinical trial to evaluate this intervention approach in patients undergoing inguinal hernia repair.

2.0 * Provide a full description of your research proposal outlining the following:

- Purpose
- Hypothesis
- Justification
- Objectives
- Research Method/Procedures
- Plan for Data Analysis

Purpose

The aim of the proposed project is to determine the feasibility of a perioperative rehabilitation program (pre- and post-surgery) and our study protocol for patients undergoing inguinal hernia repair surgery. We will answer the following question: Is a study of a peri-operative rehabilitation program feasible in terms of recruitment rate, treatment adherence, timelines, data collection procedures, patient follow-up and resources required?

Hypothesis

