Data Collection Procedures – Activities and timing of data collection are outlined in the attached document entitled 'Perioperative Rehabilitation Activity and Data Collection Protocol for Inquinal Hernia ' We will enrol patients undergoing inguinal hernia repair surgery. Participation will be voluntary, and patients will be informed of the study 8 weeks before their scheduled surgery. Once scheduled and enrolled, patients will be randomized by a research team member using Redcap. Schedule will be developed by a statistician not involved in the randomization. Participants in the intervention group will be referred to the University of Alberta's Student Physical Therapy clinic where they will undertake the pre-operative exercise and education program. The education program will include selfmanagement, expectations about the surgical and recovery process as well as quidelines for post-operative exercises. After surgery, participants in the intervention group will undergo a clinical evaluation after surgery, with the physiotherapists who will guide post-operative exercises and modify as needed. The exercises will avoid all contraindications in the acute postsurgical period, including no lifting >10kg for the first 4 weeks. The study will not impact scheduling of surgery or typical procedures. Participants in the intervention group will be booked for a short assessment with the general surgeon, remotely, to evaluate progress.

COVID-19 Implications - Since inguinal hernia repair operations have continued to be conducted despite the pandemic and physiotherapy clinics are operating following public health recommendations, unless these interventions are out on hold we will conduct this study within the typical clinical care pathway. After an initial in-person evaluation where masks will

be worn and all exercise and testing equipment is sterilized after use, all interventions will be conducted in accordance with the COVID-19 specific requirements from Public Health authorities. Telehealth options for the interventions will be available.

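### Does the last clinical outcome assessment lack a date for controls, and the 3-month follow-up a starting point?

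*Combined protocol and SAP*

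**What the plan says.** Section 2.1 (Sample) randomizes patients 1:1 to "6 weeks of prehabilitation exercises + post-surgical follow-up or else usual care". Under Data Collection Procedures, "patients will be informed of the study 8 weeks before their scheduled surgery", and after the operation "participants in the intervention group will undergo a clinical evaluation after surgery, with the physiotherapists". No equivalent session is described for controls.

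Under Measures, "Clinical outcomes will be collected at baseline, before surgery, and following the post-surgical intervention". The next sentences define persistent pain as lasting more than 3 months after surgery, by reference to a cited IASP definition. They name a 0-10 numeric scale for pain intensity and place the Carolinas Comfort Scale after the operation. Under Safety, all patients see the surgeon at 1 week, 1 month and 3 months as part of usual practice.

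The lay summary hypothesizes that "our outcome measurement protocol will provide meaningful information with high response rate and low attrition after 3 months". Appendix 2 (Follow Up) sets 80% of participants followed up at 3 months as the level for proceeding and 50% as the level for proceeding with amendments. Neither place says what the 3 months are counted from.

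Data Collection Procedures opens by saying that "Activities and timing of data collection are outlined in the attached document". The Documentation list, item 6.0, includes a file named "Data Collection Timeline and Protocol". That file was not part of the text reviewed.

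**The concern.** Three features look like gaps when the section is read closely.

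First, the last assessment is dated by an event that happens in one arm only. If the clock really were the end of the post-operative programme, controls would have no defined assessment. The arms could then be measured at different times since surgery, when pain and disability are changing quickly.

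Second, participants enter some weeks before surgery, so 3 months without a stated origin can mean two quite different dates. The Appendix 2 row for 3 months sits directly below a row for the end of prehabilitation, which does not point to surgery as the start. That row is one of the criteria for going on to a larger trial.

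Third, persistent pain is defined by duration while the named measure is an intensity score, and the Plan for Data Analysis gives no rule linking them. Patients may already have hernia-site pain before surgery (section 3.1), and a visit at exactly 3 months lies on the boundary of a definition that requires longer.

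The pilot is also meant to give "variance in our measurement protocol to inform a subsequent randomized controlled trial of the intervention". A variance pooled over assessments at mixed times would serve that purpose poorly.

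**Working it through.** The plan states no figure on this point that could be reproduced: the sample of 30 comes without alpha, power, effect size or standard deviation. The check is a comparison of the text plus calendar and binomial arithmetic.

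**1. What the text implies about the date**

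| Place | Applies to | Start of the clock |
|---|---|---|
| 2.1 Measures, last assessment | As worded, intervention arm only | End of a programme of unstated length |
| 2.1 Measures, persistent pain | All | Surgery, explicitly |
| 2.1 Measures, Carolinas Comfort Scale | All | After the operation, no week given |
| 2.1 Safety, surgeon consults | All patients | Not written; a 1-week, 1-month, 3-month series reads as post-operative |
| 2.1 lay summary and Hypothesis, attrition | All | Not written |
| Appendix 2, Follow Up | All participants | Not written |

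The one explicit 3-month anchor is surgery, and nothing in the text names entry as the start.

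**2. Calendar check**

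Three calendar months are 89 to 92 days. The lead time is an assumption taken from the plan's own figures: 8 weeks (56 days) if entry coincides with being told of the study, or 6 weeks (42 days) if it coincides with the start of prehabilitation.

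- Counted from surgery: day 89 to 92 after surgery.
- Counted from entry, 8-week lead: 89 − 56 = 33 to 92 − 56 = 36 days after surgery.
- Counted from entry, 6-week lead: 89 − 42 = 47 to 92 − 42 = 50 days after surgery.

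On the entry reading the final assessment would come about 5 to 7 weeks after surgery. That is too early to observe pain lasting more than 3 months after it, so this reading conflicts with the plan's own definition.

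**3. What the start point could do to the Appendix 2 row**

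The 80% level is 0.80 × 30 = 24 participants; the 50% level is 0.50 × 30 = 15. As an illustration, assume full enrolment and a constant loss rate. If retention 3 months (91 days) after entry is r, retention 3 months after surgery is r^((91 + lead)/91). The probabilities are exact binomial with n = 30.

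| r | P(≥24), from entry | Retention from surgery (8-wk / 6-wk lead) | P(≥24), from surgery (8-wk / 6-wk lead) | Lowest P(≥15) |
|---|---|---|---|---|
| 0.80 | 61% | 0.70 / 0.72 | 15% / 23% | 99.3% |
| 0.85 | 85% | 0.77 / 0.79 | 44% / 55% | over 99.9% |
| 0.90 | 97% | 0.84 / 0.86 | 82% / 87% | over 99.9% |
| 0.95 | over 99% | 0.92 / 0.93 | 99% / over 99% | over 99.9% |

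The start point changes the chance of meeting the top level unless loss is small. It hardly affects the chance of meeting the middle level.

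**4. Persistent pain**

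At the plan's 15%, an arm of 15 would have 0.15 × 15 = 2.25 cases, and one participant is 1/15 = 6.7 percentage points. That granularity comes from the arm size and would remain under any classification rule. Section 2.1 plans only descriptive reporting of clinical outcomes, and neither the list of feasibility outcomes nor Appendix 2 includes pain.

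**The case for a change.** The best case for a change is that it costs about three sentences and protects a pre-set decision rule. A criterion that feeds the decision on a larger trial should have its origin fixed before the data are seen. With r at 85%, the chance of meeting the 80% level is 85% counted from entry, against 44% to 55% counted from surgery. The attached timeline may settle the dates, but it would not alter a phrase that does not fit controls, and nothing shows that it contains a rule for classifying persistent pain.

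Part of this stands. The Measures wording is loose for controls, and the Appendix 2 row does not restate its origin. The rest is weaker than it looks. The contrast in retention depends on counting from entry, the less likely reading and the one at odds with the plan's pain definition. Timing is expressly delegated to an attachment, so its absence from the text reviewed cannot be called an omission from the plan. The pain definition defers to a cited source, and the assessment booklet and full proposal listed under Documentation were not available either. Whether a classification rule is missing cannot be judged from what was supplied.

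**Conclusion.** No change to the plan is called for. The most natural reading is a single post-operative assessment 3 months after surgery in both arms, and an analyst would apply it without difficulty. On that reading the arms are measured at the same time since surgery, and the feasibility conclusions, descriptive trends and variance estimates hold.

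The residual effect is small. If entry were the intended origin, the assessment would fall about 6 to 8 weeks earlier. In the illustration, the likely effect on the follow-up row is a move between proceeding and proceeding with amendments, with at least a 99% chance of reaching the 50% level in every scenario shown. No Appendix 2 criterion depends on pain.

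This rests on three assumptions: that the attached timeline agrees with the surgery-based reading, that entry falls 6 to 8 weeks before surgery, and, for the probabilities only, that loss is constant and 30 patients are enrolled. If the timeline said something different for the two arms, the point would need to be looked at again.
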